10. PROTECTION OF HUMAN SUBJECTS

The study will be carried out in compliance with the protocol, the principles laid down in the Declaration of Helsinki, in accordance with the ICH Harmonised Tripartite Guideline for GCP (to the extent applicable to the NIS setting and required by local regulations), Good Epidemiological Practice (GEP), guidelines for GPP, and relevant BI SOPs. Standard medical care (prophylactic, diagnostic and therapeutic procedures) remains in the responsibility of the treating physician of the patient.

The investigator should inform the sponsor immediately of any urgent safety measures taken to protect the study subjects against any immediate hazard, and also of any serious breaches of the protocol/ICH GCP.

10.1 STUDY APPROVAL, PATIENT INFORMATION, AND INFORMED CONSENT

This study will be initiated only after all required legal documentation has been reviewed and approved by the respective IEC and competent authority (CA) according to national and international regulations. The same applies to the implementation of changes introduced by amendments.

Prior to patient participation in the study, written informed consent must be obtained from each patient (or the patient's legally accepted representative) according to ICH GCP and to the regulatory and legal requirements. Each signature must be personally dated by each signatory and the informed consent and any additional patient information form retained by the investigator as part of the study records. A signed copy of the informed consent and any additional patient information must be given to each patient or the patient's legally accepted representative.

The patient must be informed that his/her study-related data will be used by BI in accordance with the local data protection law. The level of disclosure must also be explained to the patient.

The patient must be informed that his/her medical records may be examined by authorized monitors (CTM/CRA) or quality medicine auditors appointed by BI, by appropriate IEC members, and by inspectors from regulatory authorities.

11. MANAGEMENT AND REPORTING OF ADVERSE EVENTS/ADVERSE REACTIONS

11.1 DEFINITIONS OF ADVERSE EVENTS

Adverse event

AE is defined as any untoward medical occurrence in a patient or clinical investigation subject administered a medicinal product and which does not necessarily have a causal relationship with this treatment. An AE can therefore be any unfavourable and unintended sign (e.g., an abnormal test finding), symptom, or disease temporally associated with the use of a medicinal product, whether or not considered related to the medicinal product.

Adverse reaction

An adverse reaction is defined as a response to a medicinal product which is noxious and unintended. Response in this context means that a causal relationship between a medicinal product and an AE is at least a reasonable possibility. Adverse reactions may arise from the use of the product within or outside the terms of the marketing authorisation or from occupational exposure. Conditions of use outside the marketing authorisation include off-label use, overdose, misuse, abuse, and medication errors.

Serious adverse event

SAE is defined as any AE which

- results in death
- is life-threatening
- requires in-patient hospitalisation, or prolongation of existing hospitalisation
- results in persistent or significant disability or incapacity, or
- is a congenital anomaly/birth defect

Life-threatening in this context refers to an event in which the patient was at risk of death at the time of the event; it does not refer to an event that hypothetically might have caused death if more severe.

Medical and scientific judgment should be exercised in deciding whether other situations should be considered serious events, such as important medical events that might not be immediately life-threatening or result in death or hospitalisation but may jeopardise the patient or might require intervention to prevent one of the other outcomes listed above.

Examples of such events are intensive treatment in an emergency room or at home for allergic bronchospasm, blood dyscrasias or convulsions that do not result in hospitalisation or development of drug dependency or drug abuse. Any suspected transmission via a medicinal product of an infectious agent is also considered a serious adverse reaction

Adverse Event of Special Interest (AESI)

No AESIs have been defined for this study.

11.2 ADVERSE EVENT AND SERIOUS ADVERSE EVENT COLLECTION AND REPORTING

The investigator shall maintain and keep detailed records of all AEs in their patient files.

Collection of AEs

The study design is of non-interventional nature, and the study is conducted within the conditions of the approved marketing authorisation. Sufficient data from controlled interventional trials are available to support the evidence on the safety and efficacy of the afatinib. For this reason, the following AE collection and reporting requirements have been defined.

The following must be collected by the investigator in the eCRF from signing the informed consent onwards until the end of the study:

- From signing the informed consent onwards until 30 days after the last dose of afatinib administration:
 - *All AEs (serious and non-serious)
- From the end of the residual effect period (30 days after the last dose of afatinib administration) onwards until the individual patient's end of study:
 - All ADRs (serious and non-serious) associated with afatinib
 - *All AEs with fatal outcome

*Exemption regarding progression of underlying malignancy:

“Progressive Disease (PD) of the malignancy” is the study endpoint and will be recorded on the appropriate page of the eCRF.

During the whole study, progression of the malignancy under study (including signs and symptoms of progression) should not be reported as adverse event unless the progression is considered related to afatinib.

When there is evidence suggesting a causal relationship between afatinib and the progression of the underlying malignancy, the event must be reported as an AE on the eCRF and on the NIS AE Form.

All AEs that are to be collected including those persisting after study completion, must be followed up until they are resolved, have been sufficiently characterised, or no further information can be obtained.

Causal relationship of adverse event

The definition of an adverse reaction implies at least a reasonable possibility of a causal relationship between a suspected medicinal product and an AE. An adverse reaction, in contrast to an AE, is characterised by the fact that a causal relationship between a medicinal product and an occurrence is suspected.

Medical judgment should be used to determine the relationship, considering all relevant factors, including the pattern of reaction, temporal relationship, de-challenge or re-challenge, confounding factors such as concomitant medication, concomitant diseases, and relevant history.

Arguments that may suggest a **reasonable causal relationship** could be:

- The event is **consistent with the known pharmacology** of the drug
- The event is known to be caused by or **attributed to the drug class**
- **A plausible time to onset of the event** relative to the time of drug exposure
- Evidence that the **event is reproducible** when the drug is re-introduced
- **No medically sound alternative etiologies** that could explain the event (e.g., pre-existing or concomitant diseases, or co-medications)
- The event is typically **drug-related and infrequent in the general population** not exposed to drugs (e.g., Stevens-Johnson syndrome)
- An indication of dose-response (i.e., greater effect size if the dose is increased, smaller effect size if the dose is diminished)

Arguments that may suggest that there is **no reasonable possibility of a causal relationship** could be:

- No plausible time to onset of the event relative to the time of drug exposure is evident (e.g., pre-treatment cases, diagnosis of cancer or chronic disease within days/weeks of drug administration; an allergic reaction weeks after discontinuation of the drug concerned)
- Continuation of the event despite the withdrawal of the medication, taking into account the pharmacological properties of the compound (e.g., after 5 half-lives). Of note, this criterion may not apply to events whose time course is prolonged despite removing the original trigger.
- Additional arguments amongst those stated before, like alternative explanation (e.g., situations where other drugs or underlying diseases appear to provide a more likely explanation for the observed event than the drug concerned).
- Disappearance of the event even though the study drug treatment continues or remains unchanged.

Intensity of adverse event

The intensity of AEs should be classified and recorded according to the CTCAE criteria in the eCRF.

Pregnancy:

In rare cases, pregnancy might occur in a NIS. Once a patient has been enrolled in the study and has taken study medication, the investigator must report any drug exposure during pregnancy in a study participant within 7 days by means of Part A of the Pregnancy Monitoring Form to the sponsor's unique entry point.

Similarly, potential drug exposure during pregnancy must be reported if a partner of a male

Proprietary confidential information © 2022 Boehringer Ingelheim International GmbH or one or more of its affiliated companies

trial participant becomes pregnant. This requires a written consent of the pregnant partner. The ISF will contain the trial specific information and consent for the pregnant partner.

The outcome of the pregnancy associated with the drug exposure during pregnancy must be followed up and reported to the sponsor's unique entry point on the Pregnancy Monitoring Form (Part B).

The ISF will contain the Pregnancy Monitoring Form (Part A and B). As pregnancy itself is not to be reported as an AE, in the absence of an accompanying serious ADR and/or AESI, only the Pregnancy Monitoring Form and not the NIS AE form is to be completed. If there is a serious ADR and/or AESI associated with the pregnancy a NIS AE form must be completed in addition.

Expedited reporting of AEs and drug exposure during pregnancy

The following must be reported by the investigator on the NIS AE form and/or Pregnancy Monitoring Form from signing the informed consent onwards until the end of the study and provide o BI unique entry point:

Table 4: Expedited reporting of AEs and drug exposure during pregnancy

Type of Report	Timeline
All serious ADRs associated with afatinib Giotrif®	immediately within 24 hours
All AEs with fatal outcome in patients exposed to afatinib Giotrif® *Exemption applies	immediately within 24 hours
All non-serious ADRs associated with afatinib Giotrif®	7 calendar days
Drug exposure during pregnancy	7 calendar days

*Exemption

Death due to disease progression of the underlying malignancy is a study endpoint and the natural course of the disease. As such it is exempted from reporting as an SAE. Progression of the subject's underlying malignancy will be recorded on the appropriate pages of the eCRF only and will not be reported on the NIS AE Form. However, when there is evidence suggesting a causal relationship between afatinib and the progression of the underlying malignancy, the event must be reported as an SAE on the NIS AE Form and on the eCRF.

The same timelines apply if follow-up information becomes available for the respective events. In specific occasions, the investigator could inform the Sponsor upfront via telephone. This does not replace the requirement to complete and fax and/or email the NIS AE form.

Information required

For each reportable AE, the investigator should provide the information requested on the appropriate eCRF pages and the NIS AE form (if applicable).

11.3 REPORTING TO HEALTH AUTHORITIES

AE reporting to regulatory agencies will be done by the Marketing Authorisation Holder (MAH) according to local and international regulatory requirements.

Exemptions are described in [section 11.2](#), if applicable.

12. PLANS FOR DISSEMINATING AND COMMUNICATING STUDY RESULTS

The rights of the investigator and the sponsor with regard to the publication of the results of this study are described in the investigator contract.

The publication for study design is planned for Dec 2019, the interim analysis for the primary outcome and some secondary outcomes is planned for Dec 2022, and the publication kick-off for primary outcome is planned for Jun 2023 after the interim analysis report is completed. The final publication will be written after the final NIS report is completed in Dec 2024.

BI intends to use data from this study to prepare peer-reviewed publications and other scientific communications such as abstracts, posters, and podiums presentations.

ANNEX 1. LIST OF STAND-ALONE DOCUMENTS

Number	Document Reference Number	Date	Title
1	NA	3-Sep-2019	Informed consent form
2	NA	26-Dec-2019	Statistical and epidemiological analysis plan

ANNEX 2. ENCEPP CHECKLIST FOR STUDY PROTOCOLS

Not applicable

ANNEX 3. ADDITIONAL INFORMATION

ANNES 3.1 ECOG PERFORMANCE STATUS

Grade	Definition
0	Fully active, able to carry on all pre-disease performance without restriction
1	Restricted in physically strenuous activity but ambulatory and able to carry out work of a light or sedentary nature, e.g., light house work, office work
2	Ambulatory and capable of all self-care but unable to carry out any work activities. Up and about more than 50% of waking hours
3	Capable of only limited self-care, confined to bed or chair more than 50% of waking hours
4	Completely disabled, cannot carry on any self-care, totally confined to bed or chair
5	Dead

ANNES 3.2 PROPOSED TNM STAGE GROUPINGS

Occult carcinoma	TX	N0	M0
Stage 0	Tis	N0	M0
Stage IA1	T1a(mi)	N0	M0
	T1a	N0	M0
Stage IA2	T1b	N0	M0
Stage IA3	T1c	N0	M0
Stage IB	T2a	N0	M0
Stage IIA	T2b	N0	M0
Stage IIB	T1a-c	N1	M0
	T2a	N1	M0
	T2b	N1	M0
	T3	N0	M0
Stage IIIA	T1a-c	N2	M0
	T2a-b	N2	M0
	T3	N1	M0
	T4	N0	M0
	T4	N1	M0
Stage IIIB	T1a-c	N3	M0
	T2a-b	N3	M0
	T3	N2	M0
	T4	N2	M0
Stage IIIC	T3	N3	M0
	T4	N3	M0
Stage IVA	Any T	Any N	M1a
	Any T	Any N	M1b
Stage IVB	Any T	Any N	M1c

ANNES 3.3 RECIST GUIDELINE, VERSION 1.1

Refer to the Revised RECIST guideline (version 1.1) which was published in by Eisenhauer EA, et al. New response evaluation criteria in solid tumours: revised RECIST guideline (version 1.1) Eur J Cancer; 2009; 45; 228-247. ([R09-0262](#))

Table 1 – Time point response: patients with target (+/- non-target) disease.

Target lesions	Non-target lesions	New lesions	Overall response
CR	CR	No	CR
CR	Non-CR/non-PD	No	PR
CR	Not evaluated	No	PR
PR	Non-PD or not all evaluated	No	PR
SD	Non-PD or not all evaluated	No	SD
Not all evaluated	Non-PD	No	NE
PD	Any	Yes or No	PD
Any	PD	Yes or No	PD
Any	Any	Yes	PD

CR – complete response, PR – partial response, SD – stable disease, PD – progressive disease, and NE – inevaluable.

Table 2 – Time point response: patients with non-target disease only.

Non-target lesions	New lesions	Overall response
CR	No	CR
Non-CR/non-PD	No	Non-CR/non-PD ^a
Not all evaluated	No	NE
Unequivocal PD	Yes or No	PD
Any	Yes	PD

CR – complete response, PD – progressive disease, and NE – inevaluable.

^a ‘Non-CR/non-PD’ is preferred over ‘stable disease’ for non-target disease since SD is increasingly used as endpoint for assessment of efficacy in some trials so to assign this category when no lesions can be measured is not advised.

2. LIST OF ABBREVIATIONS

Abbreviation	/ Definition / Expansion
Acronym	
ADR	Adverse Drug Reaction
AE	Adverse Event(s)
AESI	Adverse Event of Special interest
AITS	Afatinib + investigator's choice treated set
BOR	Best overall response
BMI	Body Mass Index
CI	Confidence interval
CR	Complete response
CRF	Case Report Form
ECG	Electrocardiogram
ECOG	Eastern Cooperative Oncology Group
eCRF	Electronic Case Report Form
EGFR	Epidermal Growth Factor Receptor
ES	Enrolled set
MedDRA	Medical Dictionary for Regulatory Activities
NCI-CTCAE	National Cancer Institute-Common Terminology Criteria for Adverse Events
NIS	Non-Interventional Study
NE	Not evaluable
NSCLC	Non-small cell lung cancer
ORR	Overall response rate
OS	Overall survival
PD	Progressive disease
PR	Partial response
PT	Preferred Term
SAE	Serious adverse event
SD	Stable disease
SEAP	Statistical and Epidemiological Analysis Plan
SOC	System Organ Class

Proprietary confidential information © 2024 Boehringer Ingelheim International GmbH or one or more of its affiliated companies

Abbreviation	/ Definition / Expansion
Acronym	
T790M	Thr790Met
TEAE	Treatment-emergent adverse event
TKI	Tyrosine Kinase Inhibitor
TLF	Tables, Listings and Figures
TOT	Time on treatment
TS	Treated set
WHO-DD	World Health Organization - Drug Dictionary

Proprietary confidential information © 2024 Boehringer Ingelheim International GmbH or one or more of its affiliated companies

3. INTRODUCTION

This is a NIS to be conducted at approximately 10 sites in China where real world data are from EGFR mutation positive NSCLC patients who will initiate afatinib as first-line treatment and receiving subsequent therapy.

The primary objective of this study is to assess the time on treatment of afatinib as first-line therapy in advanced non-small cell lung cancer patients with EGFR mutation. Time on treatment (TOT) is defined from the start of afatinib treatment until the end of the afatinib treatment or death date by any cause.

This SEAP describes the detailed statistical methodology to be used in analyzing study data and outlines the statistical programming specifications for Tables, Listings and Figures (TLF). It includes the variables and analysis dataset, and manipulations as well as other types of analyses that was not mentioned in the protocol.

The analyses described in this SEAP are based upon the following study documents:

Study Protocol, Version 3.0 (Mar 08, 2022)

Electronic Case Report Form (eCRF), Version 2.0 (DEC 24, 2019)

SAS® Version 9.3 or higher will be used for all analyses.

Proprietary confidential information © 2024 Boehringer Ingelheim International GmbH or one or more of its affiliated companies

4. CHANGES IN THE PLANNED ANALYSIS OF THE STUDY

No changes of the planned analysis of the study.

[figure not shown]
5. OUTCOMES

5.1 PRIMARY OUTCOMES

- Time on treatment of afatinib (ToT) as first-line therapy in advanced non-small cell lung cancer patients with EGFR mutation. Time on treatment is defined from the start of afatinib treatment until the end of the afatinib treatment or death date by any cause. Patients that are lost to follow up or withdraw before the end of study will be censored at the time of last known contact.

5.2 SECONDARY OUTCOMES

- Overall survival (OS) from the start of afatinib until the date of death, loss to follow-up (including patient withdrawal) or end of study period
- Objective response rate (ORR) [objective response is defined as best overall response of CR and PR] according to RECIST 1.1^[1] with afatinib first-line treatment
- Adverse events (AEs), serious AEs (SAEs), afatinib-related AEs (ADRs) as indicated by incidence seriousness and intensity graded according to United States (US) national cancer institute's (NCI) (CTCAE Version 5.0)

6. GENERAL ANALYSIS DEFINITIONS

6.1 EXPOSURE

Afatinib:

Patients will be treated with afatinib 30 mg or 40 mg tablet once daily as first-line treatment as indicated in the approved labels of afatinib.

3rd generation TKI or other subsequent treatment:

Patients will be treated with 3rd generation EGFR TKI or other subsequent treatment as indicated in the approved labels.

Refer to [Section 7.6](#) and [7.7](#) for analysis details.

6.2 IMPORTANT PROTOCOL VIOLATIONS

No formal protocol deviation specification were documented in this study. Subjects who missed main informed consent, unable to provide written informed consent or not fulfil eligibility criteria will be excluded from all analysis set.

[figure not shown]

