9.7.1 Main analysis

All patients treated with afatinib will be included in the analysis of the primary outcome, Time on Treatment (TOT) on afatinib. Time on Treatment (TOT) will be evaluated by Kaplan-Meier analysis. Median Time on Treatment (TOT) and two-side 90% CI, and the quartiles will be calculated from the Kaplan-Meier curve. Patients who are lost to follow up without providing the end date of treatment with afatinib will be censored at the time of last known contact.

Overall survival (OS) will be evaluated by Kaplan-Meier analysis. Median overall survival (OS) and two-side 90% CI, and the quartiles will be calculated from the Kaplan-Meier curve. Patients who are lost to follow up (including patient withdrawal) without providing the end date of treatment will be censored at the time of last known contact. Patients who reach the end of study period without providing the end date of treatment will be censored at the end of study.

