9.7.3 Safety Analysis

All adverse events and adverse drug reactions collected per study protocol will be included and summarised in the interim safety analysis and in the final study report.

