6.3 PATIENT SETS ANALYSED

Enrolled set (ES)

The enrolled set consists of all patients who signed informed consent and fulfilled all eligibility criteria.

Treated set (TS)

Treated Set (TS) includes all patients from ES and who were dispensed medication and are documented to have taken at least one dose of first-line treatment afatinib.

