7.6 PRIMARY ANALYSES

All patients treated with afatinib will be included in the analysis of the primary outcome, Time on Treatment (TOT) on afatinib.

The TOT with afatinib is defined as time from the start of afatinib to last dose date of afatinib or death date by any cause, which comes first.

Refer to Table 7.6: 1 for the rules for determining TOT with afatinib event or censoring date. The analysis of TOT with afatinib will be performed on Treated Set (TS). Those analyses will be conducted as one of the interim analyses mentioned in [section 7.11](#).

Table 7.6: 1 Rules for determining TOT event or censoring date

Rule #	Situation	Outcome	Date of event or censoring
1	Patients lost to follow up without providing end date of treatment during afatinib treatment period	censor	Date of last known date of contact during afatinib treatment period
2	Patients still receive ongoing first-line afatinib treatment at end of study period	censor	Date of last known date of contact during first line afatinib treatment period

Proprietary confidential information © 2024 Boehringer Ingelheim International GmbH or one or more of its affiliated companies

Rule #	Situation	Outcome	Date of event of censoring
3	Other situations	event	Date of last treatment during first line afatinib treatment period

The last known date of contact will derive as follows:

For subjects who withdrew from study or became lost to follow-up, the date last known of contact will be based on the last assessment date/visit date or the date of the last dose of study drug or end of study date, whichever occurs later.

If last known of contact date is later than cut-off date, use cut-off date as last known of contact date.

Kaplan-Meier estimates and two-sided 90% confidence intervals for the 25th, median, and 75th percentiles of the survival distribution will be calculated, the Brookmeyer-Crowley method^[4] based on log-log transformation will be used to construct the 90% CI, the standard error of the Kaplan-Meier quartile estimates will be estimated using Greenwood's formula. Kaplan-Meier curves will also be produced.

For the purpose of calculating TOT, incomplete first line afatinib treatment end dates will be imputed as below:

If month and year are present and day is missing:

- If year=year of first dosing and
 - If month = month of first dose then set day to day of first dose
 - If month > month of first dose then set day to first day of month

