7.7 SECONDARY ANALYSES

7.7.1 OS from the start of afatinib until the date of death

OS is defined as the time from the start of afatinib until death for any reason. Subjects who have not died at the time of the statistical analysis will be censored at the time they were last known contact.

OS will be analyzed in a similar fashion with primary analysis. Analysis will be provided for population set TS.

The swimlane plot of overall survival by subsequent treatment will be provided.

For the purposes of displaying the subsequent treatment duration in plot, incomplete second line treatment start/end and third line treatment start dates will be imputed as below:

If month and year are present and day is missing for treatment start date:

Proprietary confidential information © 2024 Boehringer Ingelheim International GmbH or one or more of its affiliated companies

- Set day to the first day of month

If month and year are present and day is missing for treatment end date:

- If year=year of treatment start date and
 - If month = month of treatment start date then set day to last day of month
 - If month > month of first dose then set day to first day of month

For all other cases, the missing dates will not be imputed and partial dates will not be displayed on plot.

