7.10 SAFETY ANALYSIS

All the safety analysis will be performed on Treated Set (TS).

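### The SAP removes treated patients later found ineligible from the adverse event tables and the primary time-on-treatment analysis, which the protocol does not provide for

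*SAP*

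**What the plan says.** SAP 6.2 names two grounds for removing a patient from every analysis set: a consent failure, and failure to meet the entry criteria ("not fulfil eligibility criteria will be excluded from all analysis set"). Only the second is at issue here.

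SAP 6.3 repeats that condition in the set definitions. For the Enrolled Set: "The enrolled set consists of all patients who signed informed consent and fulfilled all eligibility criteria". The next set is drawn from it: "Treated Set (TS) includes all patients from ES" with at least one documented dose of first-line afatinib.

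The Treated Set is then used for TOT (SAP 7.6), OS (SAP 7.7.1: "Analysis will be provided for population set TS"), ORR (SAP 7.7.2) and resistance mechanisms (SAP 7.8.1). For safety, SAP 7.10 states: "All the safety analysis will be performed on Treated Set (TS". Disposition (SAP 7.8.2) uses the Enrolled Set.

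The protocol sets no eligibility condition at the analysis stage. Section 9.7.1 says: "All patients treated with afatinib will be included in the analysis of the primary outcome". Section 9.7.3 says: "All adverse events and adverse drug reactions collected per study protocol will be included". SAP 7.6 opens with the protocol's all-treated sentence before specifying the Treated Set. SAP 4 reports no change to the planned analysis.

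**The concern.** Eligibility is meant to be settled before enrolment, but a failed criterion can come to light after dosing. Protocol 9.8 provides for source data verification in about 30% of patients and full verification of critical data in everyone. A prior systemic therapy, or brain metastases that were symptomatic at the start of treatment, could surface this way.

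Under the SAP such a patient, although consented and exposed, counts in no estimate and no incidence table. Because disposition is based on the Enrolled Set, the patient is not counted there either, so no planned table shows how many exposed patients were removed. SAP 6.2 says that no formal protocol deviation specification exists, and protocol 9.10.5 is marked not applicable. Neither document says who makes the finding of ineligibility or when.

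The stated aim is to describe effectiveness and safety in routine practice. Incidence rates that leave out some exposed patients do not fully do that. If the removed patients tended to stop early, the TOT estimate would also look longer than it was among all patients treated.

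**Working it through.** The plan gives no figure on this point, so there is none to reproduce. The check is a comparison of definitions, followed by an illustration under stated assumptions.

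**Step 1: follow one patient.** Take a patient who consents, takes afatinib, and is later found to fail a criterion.

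- Adverse event collection: included. Protocol 11.2 starts collection at consent, with no reference to eligibility.
- Enrolled Set: excluded (SAP 6.2 and 6.3). The patient is therefore not in disposition.
- Treated Set: excluded, because it is a subset of the Enrolled Set. The patient is therefore not in TOT, OS, ORR, resistance or any adverse event table.
- Protocol 9.7.1, primary analysis: included, as a patient treated with afatinib.
- Protocol 9.7.3, safety summary: events included, as they were collected under the protocol.

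The SAP and protocol give opposite answers for TOT and for safety. SAP 7.6 gives both answers within one section. The SAP text available defines no separate safety set. It passes from 6.3 to 6.5, and nothing is inferred from that gap.

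**Step 2: share of patients affected.** N = 76 (protocol 9.5). The number treated but ineligible, k, is not stated. Assume k = 1, 2, 4 or 8. The share dropped is k/N:

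- 1/76 = 1.3%
- 2/76 = 2.6%
- 4/76 = 5.3%
- 8/76 = 10.5%

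**Step 3: effect on an incidence.** Suppose x of N treated patients have a serious adverse event and all k dropped patients are among them. The reported rate is (x − k)/(N − k), and the fall is k(N − x)/[N(N − k)]. With an assumed x = 15, the all-treated rate is 15/76 = 19.7%, and:

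- k = 1: 14/75 = 18.7%, a fall of 1.1 points
- k = 2: 13/74 = 17.6%, a fall of 2.2 points
- k = 4: 11/72 = 15.3%, a fall of 4.5 points
- k = 8: 7/68 = 10.3%, a fall of 9.4 points

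The fall cannot exceed k/N (1.3 points per patient for one patient, 5.3 for four). It reaches that limit only when x = k, that is, when no other patient had the event. If none of four dropped patients had an event, the rate would rise instead: 15/72 = 20.8%.

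**Step 4: effect on median TOT.** Take the protocol 9.5 assumption (exponential, median 12 months) for eligible patients and an assumed median m for the dropped ones. The all-treated median t solves

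[k·2^(−t/m) + (76 − k)·2^(−t/12)] / 76 = 0.5.

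- k = 4: t = 11.2 months (m = 3) or 11.6 months (m = 6)
- k = 8: t = 10.4 months (m = 3) or 11.1 months (m = 6)

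The Treated Set would show 12.0 in each case. With k = 0 nothing changes.

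**The case against.** The strongest reply is that the protocol makes eligibility a condition of being in the study: all criteria must be met (9.2.3) and are checked before enrolment (9.2). On that reading, all treated patients means all eligible treated patients, the SAP only spells this out, and SAP 4 is right to report no change. The reading is possible for TOT. It does not account for protocol 9.7.3, or for adverse event collection that runs from consent whatever the eligibility status. The qualifier in 9.7.3 (collected per protocol) does not help it, because protocol 11.2 defines that collection without reference to eligibility. If ineligible patients could never be enrolled, the exclusion in SAP 6.2 would have nothing to act on.

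Several stronger readings are tempting, and the documents do not support them:

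- **That the protocol prescribes an all-treated population for every endpoint.** The sentence in 9.7.1 is about the primary outcome only. The protocol names no such population for OS or ORR, so for those the SAP is not in conflict with it.
- **That harms in these patients go unrecorded.** Expedited reporting under protocol 11.2 does not depend on analysis sets, and SAP 7 promises listings of raw eCRF data, although it does not say for which patients. The events leave the summary tables and rates, not the record.
- **That TOT is certainly biased upward.** Symptomatic brain metastases plausibly mark a worse prognosis, but recent trial participation or age has no obvious direction. The criteria concern status at or before the start of treatment, and nothing shows that exclusions would be decided with outcomes known.

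Keeping effectiveness to the target population is a defensible choice. That supports an eligible-only analysis of effectiveness, but gives no reason to drop exposed patients from safety.

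**Conclusion.** The conflict is real for safety and for TOT. Followed as written, SAP 6.2 and 6.3 remove consented, exposed patients later found ineligible from the adverse event tables, the primary estimate and disposition. That does not match protocol 9.7.1 and 9.7.3, the opening sentence of SAP 7.6, or the statement in SAP 4. The safety part is the firmest, since it does not depend on the direction of any bias. For OS and ORR the issue is consistency only.

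The size is unknown and may be nil. The illustrations rest on assumed counts of 1 to 8 ineligible patients, an assumed 15 serious events and, for TOT, assumed medians of 3 to 6 months in the dropped patients. None of these comes from the documents. The point justifies a correction to the set definitions; it does not show that the results will mislead.

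**What to change.** 1. In SAP 6.3, define the Treated Set as all patients with valid informed consent who took at least one dose of afatinib within the study, regardless of eligibility deviations. Leave first-line out of the definition; otherwise it stays unclear whether a patient with an undisclosed prior systemic therapy belongs.
2. Use this set for safety and TOT, as the protocol states, and for OS and ORR for consistency.
3. In SAP 6.2, limit the exclusion from all sets to missing or invalid consent.
4. Base disposition on all consented patients, count eligibility deviations there, and list them by criterion. State which patients the raw data listings cover.
5. Repeat TOT, OS and ORR in eligible patients only, as a sensitivity analysis.

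The core change is about two sentences in SAP 6.2 and 6.3, with one extra set of effectiveness outputs. The price is a slightly less clean main effectiveness population. If no treated patient proves ineligible, the results do not change.
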